6.3.1.5 Definition of Intensity

The principal investigator will assess all AEs for intensity (severity) in accordance with the following standard ratings (Table 6-4):

Table 6-4 Intensity Categories

| Category | Definition |
|------------------|---|
| Mild | Ordinarily transient symptoms, does not influence performance of patient's daily activities. Treatment is not ordinarily indicated. |
| Moderate | Marked symptoms, sufficient to make the patient uncomfortable. Moderate influence on performance of patient's daily activities. Treatment may be necessary. |
| Severe | Symptoms cause considerable discomfort. Substantial influence on patient's daily activities. May be unable to continue in the study and treatment may be necessary. |
| Life threatening | Extreme limitation in activity, significant assistance required; significant medical intervention/therapy required, hospitalization or hospice care probable. |

When changes in the intensity of an AE occur more frequently than once a day, the maximum intensity for the event should be noted for that day. Any change in intensity of signs and symptoms over a number of days will be captured by recording a new AE, with the amended intensity grade and the date (and time, if known) of the change.

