6.3.1.7 Documenting, Reporting, and Eliciting Adverse Events

All AEs reported or observed during the study will be collected and recorded on the AE page of the eCRF for each patient from the date the ICF was signed until the end of their participation in the study, i.e., the patient has discontinued or completed the study.

Adverse events may be volunteered spontaneously by the patient, or discovered by the study staff during physical examinations or by asking an open, non-leading question such as, “How have you been feeling since you were last asked?” All AEs and any required remedial action will be recorded. The nature of the AE, date (and time, if known) of the AE onset, date (and time, if known) of the AE outcome to date, severity, and action taken for the AE will be documented together with the investigator’s assessment of the seriousness of the AE and causal relationship to study drug and/or study procedure.

All AEs should be recorded individually in the study patient’s own words (verbatim) unless, in the opinion of the investigator, the AEs constitute components of a recognized condition, disease or syndrome. In the latter case, the condition, disease or syndrome should be named rather than each individual symptom. The AEs will subsequently be coded using the latest version of Medical Dictionary for Regulatory Activities (MedDRA).

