7.5.8 Safety Analyses (Parts A and B)

All safety parameters will be summarized using the Safety Analysis Set.

Medical history, prior medications, concomitant medications, and compliance/exposure will be summarized by treatment group using descriptive statistics. Safety data such as reported and observed AEs, TEAEs, SAEs, clinical laboratory results, vital signs, physical examinations and neurological findings, ECGs, and the different rating scales (YMRS, C-SSRS, AIMS, BARS, and SAS) will be summarized by visit (Part A and Part B) and treatment group (Part A). Parameters planned to be collected more than once at pre-specified timepoints will be analyzed as an average of the measures for the relevant time point, including screening and baseline.

[figure not shown]
Observed and reported AE terms will be coded using the latest version of MedDRA. TEAEs will be defined as any AEs, regardless of the relationship to study drug, that occur or worsen in intensity after the first dose of study drug and within 14 days after the last dose of study drug. Study-drug-related TEAEs will be defined as any AEs that are considered by the investigator to be either possibly, probably, or definitely related to study drug. If relationship to study drug is missing, the TEAE will be considered as treatment-related. TEAEs, and SAEs will be listed summarized by SOC, PT, relationship to study drug, intensity (Part A and Part B) and treatment group (Part A). Patients who discontinue study or study drug due to an AE will be listed and summarized by SOC and PT (Parts A and B) and by treatment group (Part A).

Laboratory assessments, including hematology and chemistry, vital signs, and ECGs, will be listed and summarized by visit and time point (Parts A and B and by treatment group (Part A). Summaries will include actual and change from baseline values, incidence of abnormal values according to normal range criteria, shifts from baseline to each visit and

time point according to markedly abnormal criteria, and listings of patients meeting markedly abnormal criteria.

The observed and change from baseline in YMRS, AIMS, BARS, SAS and C-SSRS scores will be summarized by visits (Part A and B) and by treatment group (Part A).

Additional details for analyses on safety parameters will be provided in the statistical analysis plan.

A series of approximately 10 horizontal black bars of varying lengths, indicating redacted text.

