### **16.1. ADVERSE EVENTS**

Adverse Events (AEs) will be coded using MedDRA central coding dictionary currently in effect at the time of interim analysis or final Part A database lock.

Treatment emergent adverse events (TEAEs) are defined as AEs that started or worsened in severity on or after the date of the first dose of study medication and on or before the date of last dose of study medication in Part A plus one day.

All AEs with an onset date after the last dose of study medication plus one day, but before the start of Part B will be listed in the AE data listing and labelled as 'Follow-up Adverse Event'.

See [Appendix 2](#) for handling of partial or completely missing dates for AEs. In the case where it is not possible to define an AE as treatment emergent or not, the AE will be classified as the worst case, i.e., treatment emergent.

An overall summary of the number of subjects within each of the categories described in the [sub-sections 16.1.1](#) and [16.1.2](#) below will be provided as specified in the TLF shells.

Listings will include all adverse events, TEAEs and Non-TEAEs.

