### ALGORITHM FOR TREATMENT EMERGENCE OF ADVERSE EVENTS

START DATE	STOP DATE	ACTION
Known	Known	
If start date < study medication start date or start date>study medication end date + 1 day , then not TEAE
 
If study medication start date ≤ start date ≤ study medication end date + 1 day, then TEAE

	Partial	
Impute stop date as latest possible date (i.e. last day of month if day unknown or 31st December if day and month are unknown), then:
 
If start date < study med start date or start date>study med end date + 1 day, then not TEAE
 
If study med start date ≤ start date ≤ study med end date + 1 day, then TEAE

	Missing	
If start date < study med start date or start date>study med end date + 1 day, then not TEAE
 
If study med start date ≤ start date ≤ study med end date + 1 day, then TEAE

Partial, but known components show that it cannot be on or after study medication start date or cannot be before study medication end date	Known	Not TEAE
	Partial	Not TEAE

START DATE	STOP DATE	ACTION
	Missing	Not TEAE
Partial, could be on or after study medication start date but before study med end date	Known	If stop date < study med start date, then not TEAE If stop date $\geq$ study med start date, then TEAE
	Partial	Impute stop date as latest possible date (i.e. last day of month if day unknown or 31st December if day and month are unknown), then: If stop date < study med start date, then not TEAE If stop date $\geq$ study med start date, then TEAE
	Missing	Assumed TEAE
Missing	Known	If stop date < study med start date, then not TEAE If stop date $\geq$ study med start date, then TEAE
	Partial	Impute stop date as latest possible date (i.e. last day of month if day unknown or 31st December if day and month are unknown), then: If stop date < study med start date, then not TEAE If stop date $\geq$ study med start date, then TEAE
	Missing	Assumed TEAE

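### A pre-treatment adverse event that eases a grade on treatment is flagged as treatment-emergent, because intensity changes are split into new records and SAP Appendix 2 does not compare intensity

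*Protocol*

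**What the plan says.** **Recording.** Protocol 6.3.1.7 collects AEs "from the date the ICF was signed until the end of their participation in the study", so events that begin before dosing are on the AE page. Protocol 6.3.1.5 then sets the rule for intensity: "Any change in intensity of signs and symptoms over a number of days will be captured by recording a new AE". The new record carries the revised grade and is dated at the change. The one exception is for changes more frequent than once a day, where "the maximum intensity for the event should be noted for that day". The rule does not distinguish a rise in grade from a fall.

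**Definition.** SAP 16.1 defines TEAEs as "AEs that started or worsened in severity on or after the date of the first dose of study medication", up to one day after the last Part A dose. Protocol 7.5.8 covers AEs that "occur or worsen in intensity after the first dose of study drug and within 14 days after the last dose of study drug". The two windows end at different times, but both texts refer to onset or worsening, and neither mentions improvement.

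**Algorithm.** For a known start date, Appendix 2 of the SAP says: "If study medication start date ≤ start date ≤ study medication end date + 1 day, then TEAE". The same date test applies whether the stop date is known, partial or missing. When the start date is partial or missing, the stop date is also used. No row uses intensity.

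**Counting and causality.** SAP 16.1.1 counts each subject once per preferred term or system organ class and treats a missing relationship as related. Protocol 6.3.1.4 makes an AE unrelated by definition only if it starts before the first dose.

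**The concern.** Splitting an event when it worsens is what allows a date rule to pick up worsening: the worse record has its own start date, and that date falls in the window. But the split is symmetric. An improvement also produces a record with an in-window start date, and Appendix 2 cannot tell the two apart.

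The setting makes such events plausible. After consent, patients stop antidepressants and other psychotropics during a screening period of up to 2 weeks, which can be extended to no more than 28 days if the medical monitor confirms the need (Protocol 3.1.1).

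The outputs exposed are those in SAP 16.1.1: TEAE incidence by term, related TEAEs, the table of terms reaching 5% in any group, and the relative risks with their confidence intervals and p-values. There is a mirror effect after treatment. An on-treatment AE that eases later than one day after the last dose gains a new record, which SAP 16.1 labels a follow-up AE and SAP 16.1.1 summarizes by treatment group.

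**Working it through.** The plan gives no figure to reproduce here. The check applies the rule to test records and then sizes the effect under stated assumptions.

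**Step 1: the rule as written.** Take first dose on Day 1 and last dose on Day 42. Appendix 2 flags a record with a known start if 1 ≤ start day ≤ 43.

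| Record created under Protocol 6.3.1.5 | Start day | Flag |
|---|---|---|
| Original event, moderate | −5 | not TEAE |
| Same event, eased to mild | 3 | TEAE |
| Same event, worsened to severe | 3 | TEAE |
| Same event, eased to mild | 43 | TEAE |
| Same event, eased to mild | 44 | not TEAE |

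The eased and the worsened Day 3 records receive the same flag.

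**Step 2: with an intensity comparison.** Flag an in-window record only if the event has no earlier record, or the grade is higher than before first dose. The eased Day 3 record is then not a TEAE, the worsened one is, and a new event is.

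**Step 3: whether one count per term repairs it.** It prevents double counting within a subject. It does not remove a subject whose only in-window record for that term is the improvement.

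**Step 4: scale per arm.** Protocol 4.1 gives 183 patients per arm. One affected subject adds 1/183 = 0.55 percentage points to a term. The 5% table threshold is 0.05 × 183 = 9.15, so 10 subjects.

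**Step 5: effect on contrasts.** Let p be the true incidence and f the share of each arm carrying a false TEAE in that term, assumed equal across arms and independent of true events. Observed incidence = p + f(1 − p). For 4% versus 2% with f = 1%: 0.04 + 0.01 × 0.96 = 0.0496, and 0.02 + 0.01 × 0.98 = 0.0298. The ratio is 1.66 and the difference 1.98 points.

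| Assumed f | 4% v 2%: ratio | difference (points) | 10% v 5%: ratio | difference (points) |
|---|---|---|---|---|
| 0 | 2.00 | 2.00 | 2.00 | 5.00 |
| 1% | 1.66 | 1.98 | 1.83 | 4.95 |
| 2% | 1.49 | 1.96 | 1.71 | 4.90 |
| 3% | 1.39 | 1.94 | 1.62 | 4.85 |

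The difference is always (1 − f) times the true difference, so it barely moves; the ratio does. The values of f are assumptions. They correspond to 0.01 × 183 = 1.8 up to 0.03 × 183 = 5.5 subjects per arm for a single term.

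**The case against.** The strongest reply is that SAP 16.1 governs. It refers to onset or worsening, and it points to Appendix 2 only for partial or missing dates, so the appendix should not be read as overriding the definition. That shows intent but does not cure the rule. Appendix 2 contains explicit rows for fully known dates, and a split record does start in the window, so it satisfies the onset half of the definition when read literally.

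A second reply stands in full: the conditions for a false flag are demanding. Mild is the lowest grade, so a mild event that resolves creates no new record. The event must begin in screening (conditions already present at screening are medical history under SAP 12), be moderate or worse, continue to first dose, and ease without resolving inside the window. The subject must also have no genuine in-window event of the same term. Precision matters too: at 183 per arm, 4% versus 2% is about 7 versus 4 patients, with an approximate 95% interval for the relative risk of 0.6 to 6.9. A shift from 2.0 to 1.66 is small against that.

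A reader might infer that TEAE rates in every arm will be inflated by washout symptoms, that real differences will be masked, or that the split records will be rated related. The documents support none of these. They give no frequency; risk differences are nearly unchanged; and the investigator still judges causality on timing and all contributing factors. What is lost is only the automatic classification as unrelated, together with the exposure to the rule that a missing relationship counts as related. Nor does the algorithm use the start date alone in every case, since partial and missing start dates also bring in the stop date.

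Finally, the eCRF or programming specifications, not seen here, may already link split records. Even so, Appendix 2 as written makes no use of such a link.

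**Conclusion.** The rule is wrong as written. For an AE with a known start date, Appendix 2 does not implement the definition in SAP 16.1 and Protocol 7.5.8, because records created under Protocol 6.3.1.5 when an event improves pass its date test. Programmers working from the definition and from the algorithm could produce different TEAE tables.

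The consequence is possible inflation of absolute TEAE incidence and, if affected patients occur at similar rates across arms, relative risks pulled towards 1. The size is unknown and may be small; the 1% to 3% range above illustrates the effect and is not an estimate. The issue concerns descriptive safety tables and their relative risks, not the primary or key secondary efficacy analyses. It is worth correcting because the defect is clear and the correction cheap.

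**What to change.** In SAP Appendix 2, add a step ahead of the date rows:

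- Link AE records of the same event, defined as the same term with a new start on or adjoining the stop of the prior record.
- When the linked event began before first dose, flag a TEAE only if an in-window record has higher intensity than the highest pre-dose record.
- Apply the same link after treatment, so that an on-treatment AE that merely eases more than one day after the last dose is not counted as a new follow-up AE.

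Add a sentence to SAP 16.1 saying that worsening is judged on linked records, so that the definition and the algorithm agree. The cost is SAP wording and programming.

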6.3.1.6 Period of Observation for Adverse Events

For the purposes of this study, the period of observation extends from the time the patient gives his study-specific informed consent until the end of study procedures are completed.

Serious AEs occurring after completion or discontinuation of the study should be reported if they occur within 30 days after the last dose of study treatment. If the Investigator detects an SAE in a study patient after the end of the period of observation and considers the event possibly related to prior study treatment, he or she should contact the Sponsor to determine how the AE should be documented and reported.

6.3.1.7 Documenting, Reporting, and Eliciting Adverse Events

All AEs reported or observed during the study will be collected and recorded on the AE page of the eCRF for each patient from the date the ICF was signed until the end of their participation in the study, i.e., the patient has discontinued or completed the study.

Adverse events may be volunteered spontaneously by the patient, or discovered by the study staff during physical examinations or by asking an open, non-leading question such as, “How have you been feeling since you were last asked?” All AEs and any required remedial action will be recorded. The nature of the AE, date (and time, if known) of the AE onset, date (and time, if known) of the AE outcome to date, severity, and action taken for the AE will be documented together with the investigator’s assessment of the seriousness of the AE and causal relationship to study drug and/or study procedure.

All AEs should be recorded individually in the study patient’s own words (verbatim) unless, in the opinion of the investigator, the AEs constitute components of a recognized condition, disease or syndrome. In the latter case, the condition, disease or syndrome should be named rather than each individual symptom. The AEs will subsequently be coded using the latest version of Medical Dictionary for Regulatory Activities (MedDRA).

6.3.1.8 Notification About Serious or Unexpected Adverse Events

The investigator will review each SAE (Section 6.3.1.2) and evaluate the intensity and the causal relationship of the event to study drug. All SAEs will be recorded from signing of informed consent until follow-up.

The investigator is responsible for providing notification to the sponsor or designee of any SAE, whether deemed related to study drug or not, that a patient experiences during their participation in study within 24 hours of becoming aware of the event.

As a minimum requirement, the initial notification should provide the following information:

- Study number
- Patient number
- Gender
- Date of birth
- Name of investigator and full study site address
- Details of SAE
- Criterion for classification as “serious”
- Study drug code, or name if unblinded, and treatment start date and stop date, if applicable
- Date of SAE onset
- Causality assessment (if sufficient information is available to make this classification)

The sponsor will request clarification of omitted or discrepant information from the initial notification. The investigator or an authorized delegate is responsible for faxing the requested information to the sponsor within 24 hours of the sponsor's request.

Initial reports of SAEs must be followed later with detailed descriptions, including clear photocopies of other documents as necessary (e.g., hospital reports, consultant reports, autopsy reports), with the study patient's personal identifiers removed. All relevant information obtained by the investigator through review of these documents will be recorded and faxed to the sponsor within 24 hours of receipt of the information. If a new SAE Report Form is faxed, then the investigator must sign and date the form. The sponsor may also request additional information on the SAE, which the investigator or an authorized delegate must fax to the sponsor within 24 hours of the request.

The SAE reporting contact information will be provided to all participating study sites by the contract research organization (CRO) before study initiation.

6.3.1.9 Exceptions

Visits to urgent care or emergency room facilities may not warrant reporting as SAEs unless the patient is admitted to the hospital or the event meets other "serious" criteria. As discussed in Section 6.3.1.2, medical and scientific judgment should be exercised in deciding whether an AE is serious. Events that are not clearly meeting "serious" criteria can be discussed on a case-by-case basis with the medical monitor to help the investigator determine whether the event meets "serious" criteria.

6.3.1.10 Follow-Up of Adverse Events

All AEs must be reported in detail on the appropriate page in the eCRF and followed to satisfactory resolution, until the investigator deems the event to be chronic or not clinically significant, or until the patient is considered to be stable.

A follow-up telephone call will be performed for those patients with an ongoing AE which the investigator believes to be not related to study drug administration. A follow-up visit to

the study site may occur for those patients with an ongoing AE which the investigator believes to be possibly related to study drug administration.

All AEs must be reported in detail on the appropriate page in the eCRF and followed until they are resolved or stable, or judged by the investigator to be not clinically significant.

6.3.2 Safety Assessments

Safety assessments scheduled through the course of the study (Table 6–1 and Table 6-2 for Parts A and B, respectively) will include suicidality assessment by the C-SSRS, mania assessment by the YMRS, movement disorder assessment by the AIMS, BARS and SAS, vital sign measurements, ECG evaluations, and physical and neurological examination.

6.3.2.1 C-SSRS

The C-SSRS will be completed at screening, baseline, and at every subsequent scheduled clinic visit (Table 6–1 and Table 6-2 for Parts A and B, respectively). Details of the C-SSRS are presented in Section 6.1.13.

6.3.2.2 YMRS

The YMRS will be completed at screening, baseline, and at every subsequent scheduled clinic visit (Table 6–1 and Table 6-2 for Parts A and B, respectively). Details of the YMRS are presented in Section 6.1.14.

6.3.2.3 Abnormal Involuntary Movement Scale

The AIMS ([Guy, 1976](#)) measures facial and oral movements, extremity movements, and trunk movements. Seven items are rated on a scale from none (0) to severe (4). A score of “mild” (2) in 2 or more categories or a score of “moderate” or “severe” in any 1 category results in a positive AIMS score (i.e., the scores are not averaged). Additionally, overall severity is scored on the basis of severity of abnormal movements and incapacitation due to abnormal movements. The patient’s awareness of and distress caused by the abnormal movements are also noted. The AIMS is to be completed at baseline and periodically

throughout the study as specified in the schedule of events (Table 6–1 and Table 6-2 for Parts A and B, respectively).

6.3.2.4 Barnes Akathisia Rating Scale

The BARS is a rating scale for drug-induced akathisia developed by Barnes (1989). It includes the rating of observable restless movements, the subjective awareness of restlessness, and the distress associated with the akathisia. There is also a global rating for severity. The scale is completed by the investigator or an expert site-based rater after a standard examination. Objective akathisia, subjective awareness and subjective distress are rated on a 4-point scale from 0 to 3, yielding a total score from 0 to 9. The Global Clinical Assessment of Akathisia is rated separately, on a 5-point scale from 0 to 4. The BARS is to be completed at baseline and periodically throughout the study as specified in the schedule of events (Table 6–1 and Table 6-2 for Parts A and B, respectively).

